#### 4.3.5 Participant Disposition

Disposition of the study participants will be summarized descriptively for the subject categories defined below. Each table below will be populated separately for each data source and pooled across data sources for each indication.

Table 2 (Shell). Disposition of Persistent AF patients for the Safety Endpoint

| Disposition  | ThermoCool ST | ThermoCool STSF | Total        |
|--|---------------|-----------------|--------------|
| Patients meeting study inclusion criteria  | XXX (100.0%)  | XXX (100.0%)    | XXX (100.0%) |
| Patients meeting exclusion criteria*   | XXX (XX.X%)   | XXX (XX.X%)     | XXX (XX.X%)  |
| Received both the device of interest (ThermoCool ST catheter) and the comparator device (ThermoCool STSF catheter) | XXX (XX.X%)   | XXX (XX.X%)     | XXX (XX.X%)  |
| Underwent an intracardiac catheter ablation prior to the index procedure   | XXX (XX.X%)   | XXX (XX.X%)     | XXX (XX.X%)  |
| Had a surgical cardiac ablation any time prior to or at the same time as the index procedure                       | XXX (XX.X%)   | XXX (XX.X%)     | XXX (XX.X%)  |
| Had a concomitant left atrial appendage occlusion procedure at the time of the index procedure                     | XXX (XX.X%)   | XXX (XX.X%)     | XXX (XX.X%)  |
| Had a concomitant atrioventricular node ablation at the time of the index procedure                                | XXX (XX.X%)   | XXX (XX.X%)     | XXX (XX.X%)  |
| Had a prior heart transplant or long-term heart assist system implantation prior to the index procedure            | XXX (XX.X%)   | XXX (XX.X%)     | XXX (XX.X%)  |
| Incomplete follow-up**   | XXX (XX.X%)   | XXX (XX.X%)     | XXX (XX.X%)  |
| Death after 7 days from index procedure  | XXX (XX.X%)   | XXX (XX.X%)     | XXX (XX.X%)  |
| Administrative censoring (Data Extract Date-Index Date< 90 days)   | XXX (XX.X%)   | XXX (XX.X%)     | XXX (XX.X%)  |
| Patient lost to follow-up (absence of a health care encounter documented after 7 days of the index procedure)      | XXX (XX.X%)   | XXX (XX.X%)     | XXX (XX.X%)  |

|   |             |             |             |
|---|-------------|-------------|-------------|
| Patients experiencing safety events within pre-specified time periods**           | XXX (XX.X%) | XXX (XX.X%) | XXX (XX.X%) |
| Death a  | XXX (XX.X%) | XXX (XX.X%) | XXX (XX.X%) |
| Acute MI a   | XXX (XX.X%) | XXX (XX.X%) | XXX (XX.X%) |
| Acute stroke/cerebrovascular accident a                                | XXX (XX.X%) | XXX (XX.X%) | XXX (XX.X%) |
| Transient ischemic attack a  | XXX (XX.X%) | XXX (XX.X%) | XXX (XX.X%) |
| Thromboembolism a  | XXX (XX.X%) | XXX (XX.X%) | XXX (XX.X%) |
| Heart block a  | XXX (XX.X%) | XXX (XX.X%) | XXX (XX.X%) |
| Pericarditis a   | XXX (XX.X%) | XXX (XX.X%) | XXX (XX.X%) |
| Diaphragmatic paralysis a  | XXX (XX.X%) | XXX (XX.X%) | XXX (XX.X%) |
| Pneumothorax a   | XXX (XX.X%) | XXX (XX.X%) | XXX (XX.X%) |
| Pulmonary edema a  | XXX (XX.X%) | XXX (XX.X%) | XXX (XX.X%) |
| Major vascular access complication or bleeding requiring transfusion a | XXX (XX.X%) | XXX (XX.X%) | XXX (XX.X%) |
| Cardiac tamponade/perforation b  | XXX (XX.X%) | XXX (XX.X%) | XXX (XX.X%) |
| Pulmonary vein stenosis c  | XXX (XX.X%) | XXX (XX.X%) | XXX (XX.X%) |
| Atrioesophageal fistula c  | XXX (XX.X%) | XXX (XX.X%) | XXX (XX.X%) |

\* Percentage is based on patients meeting the inclusion criteria \*\*Percentage is based on patients meeting the eligibility criteria a Within 7 days of index procedure b Within 30 days of index procedure c Within 90 days of index procedure

Table 3 (Shell). Disposition of Ischemic VT patients for the Safety Endpoint

| Disposition   | ThermoCool STSF | ThermoCool ST | Total        |
|---|-----------------|---------------|--------------|
| Patients meeting study inclusion criteria   | XXX (100.0%)    | XXX (100.0%)  | XXX (100.0%) |
| Patients meeting exclusion criteria*  | XXX (XX.X%)     | XXX (XX.X%)   | XXX (XX.X%)  |
| Received both the device of interest (ThermoCool STSF) and the comparator device (ThermoCool ST)        | XXX (XX.X%)     | XXX (XX.X%)   | XXX (XX.X%)  |
| Underwent an intracardiac catheter ablation prior to the index procedure                                | XXX (XX.X%)     | XXX (XX.X%)   | XXX (XX.X%)  |
| Had a surgical cardiac ablation prior to or at the time of the index procedure                          | XXX (XX.X%)     | XXX (XX.X%)   | XXX (XX.X%)  |
| Had a prior heart transplant or long-term heart assist system implantation prior to the index procedure | XXX (XX.X%)     | XXX (XX.X%)   | XXX (XX.X%)  |
| Patients with less than 7 days of follow-up due to administrative censoring                             | XXX (XX.X%)     | XXX (XX.X%)   | XXX (XX.X%)  |
| Patients experiencing safety events within 7 days**   | XXX (XX.X%)     | XXX (XX.X%)   | XXX (XX.X%)  |
| Death   | XXX (XX.X%)     | XXX (XX.X%)   | XXX (XX.X%)  |
| Acute MI  | XXX (XX.X%)     | XXX (XX.X%)   | XXX (XX.X%)  |
| Acute stroke  | XXX (XX.X%)     | XXX (XX.X%)   | XXX (XX.X%)  |
| Deep venous thrombosis  | XXX (XX.X%)     | XXX (XX.X%)   | XXX (XX.X%)  |
| Pulmonary embolus   | XXX (XX.X%)     | XXX (XX.X%)   | XXX (XX.X%)  |

|  |             |             |             |
|--|-------------|-------------|-------------|
| Complete heart block                             | XXX (XX.X%) | XXX (XX.X%) | XXX (XX.X%) |
| Pericardial effusion with hemodynamic compromise | XXX (XX.X%) | XXX (XX.X%) | XXX (XX.X%) |
| Cardiac perforation                              | XXX (XX.X%) | XXX (XX.X%) | XXX (XX.X%) |
| New acute severe mitral or aortic regurgitation  | XXX (XX.X%) | XXX (XX.X%) | XXX (XX.X%) |
| Arterial dissection                              | XXX (XX.X%) | XXX (XX.X%) | XXX (XX.X%) |
| Vascular injury                                  | XXX (XX.X%) | XXX (XX.X%) | XXX (XX.X%) |

\* Percentage is based on patients meeting the inclusion criteria \*\*Percentage is based on patients meeting the eligibility criteria

#### 4.4 Missing Data

Missing data on the outcomes can occur due to loss to follow-up. These patients will be censored at the time at which follow-up terminated. Missing data on the treatment variable is addressed in the study inclusion criteria. For missing covariate information an informative missing data approach is adopted, such that for nominal variables we create a separate level to indicate a missing value, and for continuous variables the mean is imputed and indicator variable for missing values on that variable is created [2]. The variables with levels representing missing data and missing data indicator variables were included in the propensity score model unless there was a positivity violation (i.e., there are no observations in one of the device arms with missing data on a particular covariate).

#### 4.5 Observational Study Conduct

Covariate balancing methods are used to address the comparisons of a subject device to the comparator device. In our approach, covariate balancing is kept separate from the analysis [3]. A physical separation between the design and analysis is put in place [4-6], such that the person responsible for covariate balancing does not have access to the outcome data. Specifically, one individual created the analytical dataset at each institution (Mercy, Mayo Clinic). Information on the outcome variable was removed from the analytical datasets while retaining a linkage id, and these outcome-removed datasets were provided to an independent statistician who balanced the data. The balanced data will be linked back to the outcome at the home institution in order to perform the outcome analysis (section 4.7). The pooled analyses (sections 4.7.3 & 4.7.4) are relatively straightforward and will be performed by an individual at the Mercy organization.

#### 4.6 Covariate Balancing

The propensity score (PS) will be used for covariate balancing. The methodology described in this section is applied within each data source (Mercy, Mayo Clinic) for both safety and effectiveness endpoints for persistent AF. The methodology will be applied separately within Mercy and Mayo Clinic since this study will use a distributed data network approach where each healthcare system analyzes their own data separately using common methods and treatment effect estimates are pooled subsequently.

#### 4.6.1 Propensity Score Calculation

The method for calculating the propensity score is a multivariable logistic regression model, with K-1 dummy variables for nominal covariates with K levels, and a single variable for each continuous covariate (linear specification).

#### 4.6.2 Method for Covariate Balancing

We considered several PS methods to maximize balance [7] (see appendix, tables 1-4). For ischemic VT, none of the methods considered adequately balanced the data, therefore a comparative design was not pursued in favor of single arm design using a performance goal [8]. For persistent AF a singular method that minimizes imbalance across the two data sources was selected, average treatment effect on the treated weights [9] with weight trimming/winsorizing [10]. Specifically, patients receiving the subject device receive a weight of 1 and those receiving the comparator device (c) receive a weight based on the odds,  $w_i = \frac{\hat{e}_i}{1-\hat{e}_i}$ , where  $\hat{e}_i$  = estimated propensity score for patient  $i = 1, \dots, n_c$ . Furthermore, patient weights in the comparator group only are trimmed/winsorized at the 95th percentile of the weight distribution (i.e., all weights with value above the 95th percentile are set equal to the 95th percentile).

When used with logistic regression to estimate the propensity score, weight trimming has been shown to reduce bias in estimating the treatment effect when the model is mis-specified due to non-linear and non-additive effects, as well as to increase precision of the estimated treatment effects [10]. Use of untrimmed ATT weights has been shown unbiased in simulation studies in estimating the risk difference using survival data [11].

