### 1.2 Exploratory Objectives

The exploratory objectives are:

- To describe the effectiveness of ablation with the ThermoCool ST catheter relative to ThermoCool STSF for the treatment of persistent AF using the propensity score balanced data.

- To describe the effectiveness of ablation with the ThermoCool STSF catheter for the treatment of ischemic VT using the unadjusted data.
- To describe the safety of ablation with the ThermoCool STSF catheter for the treatment of overall VT on a composite safety endpoint using the unadjusted data. The overall VT population will be identified using the same criteria as ischemic VT except removing the requirement of prior MI.
- To describe the safety of ablation with the ThermoCool STSF catheter in a subgroup that excludes non-ischemic cardiomyopathy patients using a composite safety endpoint in the ischemic VT population using the unadjusted data.
- Explore the sensitivity of the safety results for persistent AF to hospital bed size. Remove hospital bed size as a balancing variable for patients with persistent AF in the Mayo data source. Perform the balanced outcome analysis with this modification in Mayo and recalculate an average difference (all Mercy hospital bed sizes were above the prespecified bed size cut point of 500 so this covariate was not included in the Mercy propensity score model).
- Explore the sensitivity of the safety results for ischemic VT by performing an outcome analysis comparing the ThermoCool STSF group to the ST group using the balanced data.
- Perform exploratory subgroup analyses among patients with a prior prescription of class I or III AAD before the index ablation procedure for the persistent AF population using propensity score balanced data.

Determinations about comparative effectiveness and safety of these exploratory objectives will not be based on hypothesis tests, rather examination of point and confidence interval estimates within each group and differences.

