#### 4. Analytic Methods to Meet the Primary and Exploratory Objectives

##### 4.1. Treatment

In the persistent AF analysis the subject device group is the ThermoCool ST catheter and the comparison group is the ThermoCool STSF catheter. In the ischemic VT analysis the subject device group is the ThermoCool STSF catheter.

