#### 4.6.3. Definitions of Absolute Standardized Differences

Balance is evaluated using absolute standardized differences [12]. When evaluating balance before any covariate balancing for continuous covariates for the subject device (s) and comparator device (c) we use  $\hat{d} = \frac{|\bar{x}_s - \bar{x}_c|}{\sqrt{\frac{\hat{v}(\bar{x}_s) + \hat{v}(\bar{x}_c)}{2}}}$  and for binary covariates  $\hat{d} = \frac{|\hat{p}_s - \hat{p}_c|}{\sqrt{\frac{\hat{p}_s(1-\hat{p}_s) + \hat{p}_c(1-\hat{p}_c)}{2}}}$ .

When using weights, covariate balance for a continuous covariate we replace the means and variance of the comparator group with weighted versions of those estimates [13]  $\hat{d}^w = \frac{|\bar{x}_s - \bar{x}_c^w|}{\sqrt{\frac{\hat{v}(\bar{x}_s) + \hat{v}^w(\bar{x}_c)}{2}}}$ , where  $\bar{x}_c^w = \frac{\sum_{i=1}^{n_c} w_i x_i}{\sum_{i=1}^{n_c} w_i}$ ,  $\hat{v}^w(\bar{x}_c) = \frac{\sum_{i=1}^{n_c} w_i}{(\sum_{i=1}^{n_c} w_i)^2 - \sum_{i=1}^{n_c} w_i^2} \sum_{i=1}^{n_c} w_i (x_i - \bar{x}_c^w)^2$ . For a categorical covariate we replace the proportion of the comparator group with a weighted version of that estimate [18]  $\hat{d}^w = \frac{|\hat{p}_s - \hat{p}_c^w|}{\sqrt{\frac{\hat{p}_s(1-\hat{p}_s) + \hat{p}_c^w(1-\hat{p}_c^w)}{2}}}$ , where  $\hat{p}_c^w = \frac{\sum_{i=1}^{n_c} w_i x_i}{\sum_{i=1}^{n_c} w_i}$ .

Nominal variables with more than two categories are summarized using generalizations of the above for binary covariates [14].

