| Mean ASD                       |             |             |             | 0.29  | 0.65  | 0.48  | 0.21  | 0.18  | 0.18  |

Note: When using stratification, covariate balance for a particular covariate is the average balance across strata ( $k = 1, \dots, 5; K = 5$ ), calculated using  $\sum_{k=1}^K w_{(k)} \hat{d}_{(k)}$ , where  $w_{(k)} = \frac{n_{s(k)}}{n_s}$  and  $n_s$  is the number of patients with the subject device.

Table 3. Ischemic VT: Mercy Balance Results

| Variable                | Value     | STSF       | ST         | Crude | Strata | Untrimmed | Trimmed
99 | Trimmed
95 | Trimmed
90 |
|-------------------------|-----------|------------|------------|-------|--------|-----------|---------------|---------------|---------------|
| Age (cat)               |           |            |            | 0.581 | 1.082  | 1.151     | 1.151         | 0.778         | 0.773         |
|                         | <65       | 8 (22.9%)  | 11 (47.8%) |       |        |           |               |               |               |
|                         | 65-74     | 19 (54.3%) | 7 (30.4%)  |       |        |           |               |               |               |
|                         | >=75      | 8 (22.9%)  | 5 (21.7%)  |       |        |           |               |               |               |
| Sex                     |           |            |            | 0.372 | NA     | 0.649     | 0.649         | 0.649         | 0.649         |
|                         | Male      | 33 (94.3%) | 19 (82.6%) |       |        |           |               |               |               |
|                         | Female    | 2 (5.7%)   | 4 (17.4%)  |       |        |           |               |               |               |
| Race                    |           |            |            | 0.080 | NA     | 0.298     | 0.298         | 0.296         | 0.295         |
|                         | White     | 34 (97.1%) | 22 (95.7%) |       |        |           |               |               |               |
|                         | Non-White | 1 (2.9%)   | 1 (4.3%)   |       |        |           |               |               |               |
| Index Year              |           |            |            | 0.687 | 0.805  | 0.593     | 0.593         | 0.343         | 0.241         |
|                         | 2014-18   | 10 (28.6%) | 14 (60.9%) |       |        |           |               |               |               |

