| 0.20          |  |  | 9    | 9    | 14   | 14   | 10   | 9    |
| Mean ASD      |  |  | 0.37 | 0.60 | 0.45 | 0.45 | 0.33 | 0.31 |

Note: When using stratification, covariate balance for a particular covariate is the average balance across strata ( $k = 1, \dots, 5; K = 5$ ), calculated using  $\sum_{k=1}^K w_{(k)} \hat{d}_{(k)}$ , where  $w_{(k)} = \frac{n_{s(k)}}{n_s}$  and  $n_s$  is the number of patients with the subject device. Elixhauser not included as a covariate in the propensity score model because for STSF there were 0 instances of patients with scores  $\leq 3$ .

Table 4. Ischemic VT: Mayo Balance Results

| Variable             | Value     | STSF       | ST         | Crude | Strata | Untrimmed | Trimmed
99 | Trimmed
95 | Trimmed
90 |
|----------------------|-----------|------------|------------|-------|--------|-----------|---------------|---------------|---------------|
| Age (cat)            |           |            |            | 0.229 | 1.581  | 0.828     | 0.589         | 0.108         | 0.124         |
|                      | <65       | 11 (31.4%) | 31 (36.9%) |       |        |           |               |               |               |
|                      | 65-74     | 13 (37.1%) | 35 (41.7%) |       |        |           |               |               |               |
|                      | >=75      | 11 (31.4%) | 18 (21.4%) |       |        |           |               |               |               |
| Sex                  |           |            |            | 0.085 | 0.542  | 0.537     | 0.508         | 0.141         | 0.123         |
|                      | Male      | 31 (88.6%) | 72 (85.7%) |       |        |           |               |               |               |
|                      | Female    | 4 (11.4%)  | 12 (14.3%) |       |        |           |               |               |               |
| Race                 |           |            |            | 0.010 | 0.315  | 0.315     | 0.288         | 0.036         | 0.051         |
|                      | White     | 33 (94.3%) | 79 (94.0%) |       |        |           |               |               |               |
|                      | Non-White | 2 (5.7%)   | 5 (6.0%)   |       |        |           |               |               |               |
| Elixhauser Index     |           |            |            | 0.151 | 1.886  | 1.642     | 0.949         | 0.078         | 0.059         |

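### The weighted columns of the ischemic VT balance tables reweight STSF to resemble ST, although the SAP makes STSF the VT subject device; the cited weighting evidence therefore concerns the wrong target group

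*SAP*

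**What the plan says.** Section 4.1 of the SAP states: "In the ischemic VT analysis the subject device group is the ThermoCool STSF catheter". The sample size table in Section 3 agrees, labelling STSF as test and ST as reference for ischemic VT, and the VT exclusion criteria in Section 2 call STSF the device of interest.

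Section 4.6.2 describes the weighting: "patients receiving the subject device receive a weight of 1 and those receiving the comparator device (c) receive a weight based on the odds". That sentence is written for persistent AF, where ST is the subject device. Section 4.6.3 defines the weighted absolute standardized difference (ASD) in general terms, with the subject proportion left as observed; for the other arm, "we replace the proportion of the comparator group with a weighted version of that estimate".

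On VT, Section 4.6.2 concludes: "For ischemic VT, none of the methods considered adequately balanced the data". The evidence is in the appendix ("Table 3. Ischemic VT: Mercy Balance Results" and "Table 4. Ischemic VT: Mayo Balance Results"), which has a stratification column and four weighting columns: untrimmed, and trimmed at the 99th, 95th and 90th percentiles. Sections 4.7 and 6 (item 3) repeat the balance rationale. Section 6 adds a second reason, that one or more catheter groups might have no events. Section 1.2 keeps an exploratory VT safety analysis "comparing the ThermoCool STSF group to the ST group using the balanced data".

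**The concern.** Under the SAP's own definitions, the VT weighting columns should leave STSF as observed and reweight ST to resemble it. That is the contrast for the patients in whom the label is sought. Nothing in the SAP says that ST is the VT target. If the tables were produced with the AF coding carried over (ST as subject), their weighted ASDs answer a different question.

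Two things depend on this. First, the weighting columns are part of the evidence for replacing a comparison with a single-arm test against a performance goal. Second, the exploratory VT comparison in 1.2 refers to balanced data without naming a target group. If it took over these weights, it would estimate the difference in ST recipients.

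**Working it through.** **Formula (4.6.3).** For a binary covariate, ASD = |p_fixed − p_w| / √{[p_fixed(1 − p_fixed) + p_w(1 − p_w)]/2}. Here p_fixed is the raw share in the weight-1 arm and p_w the weighted share in the other arm. If p_w = 0, this reduces to √[2p/(1 − p)] with p = p_fixed.

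**Crude values first.** Mercy female, STSF 2/35 and ST 4/23: 0.372 (printed 0.372). Mercy hypertension, 34/35 and 20/23: 0.383 (printed 0.383). Mercy valve replacement, 1/35 and 1/23: 0.080 (printed 0.080). Mayo Elixhauser ≤3, 1/35 and 5/84: 0.151 (printed 0.151). The formula and counts are being read correctly.

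**Mercy (Table 3).** Three rows print the same value in all four weighting columns. Compare them with the zero-share limit for each candidate weight-1 arm:

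| Row | Printed, all four | ST at weight 1, p_w = 0 | STSF at weight 1, p_w = 0 |
|---|---|---|---|
| Female | 0.649 | √(8/19) = 0.649 (4/23) | 0.348 (2/35) |
| No hypertension | 0.548 | √(6/20) = 0.548 (3/23) | 0.243 (1/35) |
| Valve replacement | 0.301 | √(2/22) = 0.3015 (1/23) | 0.243 (1/35) |

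With ST at weight 1, the few STSF patients in these categories have almost no weight, so trimming the large weights changes nothing visible. (For valve replacement, 0.301 corresponds to a share just above zero.) With STSF at weight 1, the printed values would need weighted ST shares of 29.1%, 19.5% and 10.2%. Those shares would have to stay put under every trim level while age, index year and ICD/pacemaker move. That is not credible.

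**Mayo (Table 4), size of the largest weight.** Solving the formula for p_w with ST at weight 1:

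| Row | Raw STSF | Untrimmed ASD → share | Trimmed 99 ASD → share |
|---|---|---|---|
| Elixhauser ≤3 | 1/35 | 1.642 → 67.1% | 0.949 → 42.8% |
| No CHF | 2/35 | 1.373 → 67.3% | 0.745 → 43.1% |
| No hypertension | 5/35 | 1.332 → 67.5% | 0.716 → 43.5% |

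Only one STSF patient has Elixhauser ≤3, so that patient carries about two thirds of the untrimmed STSF weight.

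**Mayo, common-factor check.** If the 99th-percentile trim caps only that largest weight, every share that excludes this patient must rise by the same factor: (1 − 0.4275)/(1 − 0.6705) = 0.5725/0.3295 = 1.737. The table gives the ratio of trimmed-99 share to untrimmed share. With ST at weight 1 it is shown as an interval that allows for rounding of the printed ASDs:

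| Row | ST at weight 1 | STSF at weight 1 |
|---|---|---|
| Non-white | 1.681–1.753 | 1.83–1.92 |
| Diabetes | 1.726–1.763 | 4.05–4.35 |
| Anemia | 1.725–1.757 | 5.8–6.3 |
| Valve replacement | 1.715–1.765 | 1.89–1.95 |
| No class I/III AAD | 1.730–1.760 | 1.31–1.32 |
| Female | 1.725–1.796 | no low-share solution for the untrimmed value |
| No ICD/pacemaker | 1.717–1.777 | no low-share solution for the untrimmed value |
| Years 2019–21 | 1.729–1.744 | not coherent either |

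Every interval in the middle column contains 1.737. The right-hand column has no common factor. Both VT tables therefore hold ST at weight 1 and reweight STSF in all four weighting columns.

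**What this direction asks of the data.** At Mayo, 5 STSF patients from 2014–18 must stand for 68 ST patients. At Mercy, 2 STSF patients without an ICD or pacemaker (33 of 35 have one) must stand for 11 ST patients (12 of 23 have one).

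**The case against.** The arithmetic is hard to dispute, but what follows from it is limited.

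- **The weighting rule is written for AF.** Section 4.6 applies the method to persistent AF, and the SAP adopts no VT weighting method. This stands as far as it goes. The ASD definitions are general, however, and Sections 2, 3 and 4.1 all make STSF the VT device under study, so the tables still conflict with the text.
- **A reader might infer that the comparative design was wrongly dropped.** The documents do not support that. The stratification column also balances poorly (mean ASD 0.60 at Mercy and 0.98 at Mayo), and its direction cannot be determined from the table. Possible zero events is a separate reason that weight direction does not touch. Rough simulation from the printed margins, assuming independent covariates and trimming at the 95th percentile, leaves Mercy with a mean ASD of about 0.22–0.23 and about 8 ASDs above 0.20 when STSF is the target. Mayo's mean falls to about 0.14, against 0.16 printed. These figures are only indicative: run in the ST direction, the simulation gives 0.24–0.25 at Mercy against 0.33 printed, so it probably understates real imbalance.
- **A reader might also infer that the choice cost power, leaving only 57%.** That is not shown. Assume 7.5% in both arms, all 70 and 107 patients, one-sided 5%, and a margin of 0.07 to 0.075 (an assumption). The standard error is √[0.075 × 0.925 × (1/70 + 1/107)] = 0.0405, giving power of about 53% to 58% before any loss from weighting.
- **No confirmatory estimate uses these weights.** The VT primary test is an unadjusted proportion against a performance goal. This stands.

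**Conclusion.** The four weighting columns of Tables 3 and 4 are in the opposite direction to the SAP's VT subject device. The result rests on the printed counts and ASDs, the formula in 4.6.3 and, for the Mayo factor, the assumption that the 99th-percentile trim caps only one patient's weight. The agreement of all the rows tested supports that assumption.

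The weighting part of the balance rationale therefore describes ST recipients, and so would the exploratory comparison in 1.2 if it reused these weights. Balance with STSF as the target cannot be computed without patient-level data. The single-arm decision may stand; what is lacking is correct weighting evidence for it. The primary VT result is unaffected numerically. The correction should be made, but it does not invalidate the design.

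**What to change.** Before the balanced data are linked to outcomes:

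1. Have the independent statistician re-run Tables 3 and 4 with STSF at weight 1 and ST weighted by e/(1 − e), where e is the estimated probability of receiving STSF. State the direction used for the stratification column as well.
2. Replace both tables, with a note naming the target group.
3. Confirm or revise the balance rationale in 4.6.2, 4.7 and Section 6 item 3 on the new results.
4. In 1.2, name STSF recipients as the target group for the exploratory VT comparison. If ST was meant as the target, say so and justify it.

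The cost is one outcome-blind re-run of existing code with the arms swapped, two replaced tables and a few lines of text. No new data are needed.
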